#### **5.2 Dose Modification**

The decision to enroll the sequential cohort at the next dose level will be based on the safety data from previous dose cohorts. Dose escalation will depend on the emergence of dose-limiting AEs and review of the safety data. Progression to the next higher dose will only occur if the previous dose level was deemed to be well tolerated by the SRC. Safety data sets to be reviewed by the SRC for dose escalation determination will include all available data up to 96 hours post-dosing for subjects enrolled into each dose-level cohort. A minimum of 7 subjects' data will be evaluated to make dose escalation decisions. Decisions to proceed to the next cohort will be based upon the recommendation of the SRC and agreed upon with the Investigator and Sponsor.

Doses will be flexible during the study to allow for reductions in the planned escalation based on safety. When it is not appropriate to escalate the dose, then the same dose, a previous dose, or an intermediate dose may be given following discussion between the Investigator and Sponsor.

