# 9.1.4 Dose-limiting Adverse Events

Dose-limiting AEs are defined as clinically significant AEs or abnormal laboratory values that are Grade 3 or 4 in severity, based on toxicity grading scales as specified in FDA's Guidance for Industry and Investigators – Toxicity Grading Scale for Healthy Adult and Adolescent Volunteers Enrolled in Preventive Vaccine Clinical Trials.

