# 9.1.5 Adverse Events of Special Interest

The following signs of drug toxicity will be deemed to be of special interest and may be dose-limiting:

- Sustained respiratory depression that results in oxygen saturation below 92%.
- Seizure
- Protracted (> 1 hour) nausea and vomiting.
- Any AE deemed by the Investigator to be dose-limiting or  $\geq$  Grade 3 in intensity.
- Clinical investigations indicating signs of drug-induced liver injury based on the following criteria from FDA guidance:

- Alanine aminotransferase (ALT) or aspartate transaminase (AST) > 8 x the upper limit of normal (ULN).
- $\circ$  ALT or AST > 5 x ULN for more than 2 weeks.
- $\circ$  ALT or AST > 3 x ULN and (total bilirubin > 2 x ULN or international normalized ratio > 1.5).
- ALT or AST > 3 x ULN with the appearance of fatigue, nausea, vomiting, right upper quadrant pain or tenderness, fever, rash, and/or eosinophilia (> 5%).
- Any clinically significant findings of blood chemistry and hematology.

Depending on the severity of these and/or other AEs or the occurrence of more than 1 AE in the same subject, the subject(s) may be unblinded if it is deemed necessary for the treatment of AEs.

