## 9.1.6 Severity

The severity (intensity) of each AE must be assessed according to the following classification:

- Mild: does not interfere with routine activities.
- Moderate: interferes with routine activities.
- Severe: subject is unable to perform routine activities.

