## 10.5 Safety Analysis

All safety data from the study will be listed by subject, dose, and cohort. Changes in safety assessments from screening to post-dose measurements will be assessed using summary statistics (mean, minimum, maximum, standard deviation, and corresponding sample size [N] for continuous variables, and frequency of category shifts from screening to post-study for discrete variables) for each part/cohort. Additionally, summary statistics for vital signs (blood pressure, pulse, pulse oximetry, and respiratory rate) and oral temperature will be reported.

Adverse events will be coded using the toxicity grading scale tables as specified in Guidance for Industry and Investigators – Toxicity Grading Scale for Healthy Adult and Adolescent Volunteers Enrolled in Preventive Vaccine Clinical Trials and Medical Dictionary for Regulatory Activities terminology. The AEs will be summarized by dose and visit and overall. The AEs will be tabulated and summarized by body system, preferred term, severity, frequency, and relationship to study drug. A listing of SAEs will be provided.

Change from screening in clinical laboratory parameters and vital sign parameters will be summarized by visit and overall. Shift tables for key safety parameters including clinical lab investigations will be presented. Frequency descriptors for the safety analyses will be reported as needed.

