#### 4.1.2.2 Coding of Adverse Event Terms

Adverse event terms (Investigator terms) will be coded to a lowest level term (LLT), preferred term (PT), high level term (HLT), high level group term (HLGT) and a system organ class (SOC) according to the Medical Dictionary for Regulatory Activities (MedDRA) dictionary, Version 26.1 or later, depending on the latest version available during the study.

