### 6.8.3 Laboratory Parameters

The laboratory parameters described in Section 4.1.3 will be summarized and listed.

The summary tables of hematology, coagulation and biochemistry results will present summary statistics for each laboratory parameter within the specific test panel by treatment group. For each parameter, summaries will be presented for the baseline and each scheduled post-baseline visit. In addition, summaries will be presented for the change from baseline values at each scheduled post-baseline visit. Refer to Section 4.1.3 for the handling of character results.

The summary of hematology, coagulation, and biochemistry shift tables will present summaries for the shifts in the result classifications ('Normal', 'Low', 'High') from the baseline to each of the scheduled post-baseline visit for each parameter with a defined reference range, within the specific test panel.

The listings of hematology, coagulation and biochemistry data will include all laboratory data (collected at scheduled and unscheduled visits) in the clinical database. The listings will present all the information (fields) that is available in the laboratory dataset. In addition, the observation that was used as the baseline records (values) for each parameter will be flagged, the change from baseline value and the derived result classification (based on the normal ranges where applicable) at each post-baseline visit will be presented.

The summary of urinalysis table will present the number and percentage of subjects for each of the result classifications (Normal, Abnormal NCS and Abnormal CS) for the baseline, each scheduled post-baseline per parameter.

The listing of urinalysis (including microscopy) data will include all laboratory data (collected at scheduled and unscheduled visits) in the clinical database. The listings will present all the information (fields) that is available in the laboratory dataset. In addition, the observation that was used as the baseline record (value) for each parameter will be flagged.

The FSH parameters will be listed as part of the pregnancy listing.

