## 7. Changes to the Planned Analyses

### 7.1 Changes to the Analyses Described in the Study Protocol and Protocol Amendments

Not applicable.

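### Protocol 10.5 calls for FDA toxicity grading of adverse events, the SAP omits it without declaring a change, and no planned summary table counts by dose the subjects who meet the dose-limiting or ULN-multiple criteria

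*Protocol*

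**What the plan says.** **Protocol.** Section 10.5 pairs MedDRA with the FDA toxicity scale: "Adverse events will be coded using the toxicity grading scale tables as specified in Guidance". Section 9.1.4 uses the same scale: "Dose-limiting AEs are defined as clinically significant AEs or abnormal laboratory values that are Grade 3 or 4 in severity". Section 5.2 gives those events their role: "Dose escalation will depend on the emergence of dose-limiting AEs and review of the safety data". Section 5.3 also words its halting rules in Grades 2 and 3. Section 9.1.5 sets its liver criteria in multiples of the upper limit of normal, one of them combined across analytes: "ALT or AST > 3 x ULN and (total bilirubin > 2 x ULN or international normalized ratio > 1.5". Section 9.1.6 uses a different scale for severity, with three functional levels, of which the highest is "Severe: subject is unable to perform routine activities".

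**SAP.** Section 4.1.2.2 codes event terms "according to the Medical Dictionary for Regulatory Activities (MedDRA) dictionary, Version 26.1 or later" and names no toxicity scale. Sections 4.1.2.1 and 6.8.2 work with the reported rating of Mild, Moderate or Severe. Section 4.1.3 classes quantitative laboratory results only against the normal range, and section 6.8.3 tabulates "the shifts in the result classifications ('Normal', 'Low', 'High') from the baseline to each of the scheduled post-baseline visit". The table list in Attachment 1 has no table of toxicity grade, dose-limiting events, events of special interest or ULN multiples. Section 7.1, on changes from the protocol, reads "Not applicable".

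**The concern.** Safety and tolerability by dose is the primary objective. The protocol sets out in advance which events it treats as dose-limiting or of special interest, and it does so by toxicity grade and ULN multiple. A study report built from the planned tables would show how many subjects had an event the investigator called severe, and how many had a result outside the normal range. It would not show, dose by dose, how many met the protocol's own criteria.

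There is also a traceability problem. The SAP presents itself as a complete specification and records no change from the protocol, yet one element of the adverse event analysis in 10.5 is absent.

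**Working it through.** The documents give no figure on this point, and no formula applies. The check compares the protocol's criteria with each planned output that might report them.

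| Protocol criterion | Closest planned SAP table | Can it be counted there? |
|---|---|---|
| Toxicity grade of an event (10.5) | Severity table, Mild/Moderate/Severe (6.8.2) | No, different scale |
| Dose-limiting event, Grade 3 or 4 (9.1.4) | None | No, listing flag only |
| Event of special interest (9.1.5) | None | No, listing flag only |
| ALT or AST above 3, 5 or 8 x ULN (9.1.5) | Low/Normal/High shifts (6.8.3) | No, one High cell |
| ALT/AST combined with bilirubin or INR (9.1.5) | None, since each analyte is tabulated separately | No |

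1. *Denominators.* Three cohorts of 6 active and 2 placebo subjects give 3 x 6 = 18 active and 3 x 2 = 6 pooled placebo.

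2. *Severity rating as a stand-in for grade.* The two scales have different anchors. A laboratory abnormality that the toxicity scale puts at Grade 3, in a subject who feels well and carries on as usual, is Mild under 9.1.6. The functional scale also stops at one top level, so Grade 4 has no cell of its own.

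3. *Laboratory shifts.* Take ALT at 1.1 x ULN and at 9 x ULN. Both exceed 1 x ULN, so both are High. The first is below 3 x ULN and meets no criterion; the second is above 8 x ULN and meets one. They share a cell. Protocol 4.3 excludes ALT only above 1.5 x ULN, so a subject may enter at 1.5 x ULN if that is judged not clinically significant. A rise from there to 9 x ULN would be tabulated as High to High, that is, as no shift.

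4. *Laboratory summary statistics.* The biochemistry tables give the maximum by dose and visit. The ULN is not printed beside it, and each analyte stands alone, so the combined criterion cannot be seen.

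5. *Adverse event tables.* Protocol 8.2.3 sends every clinically significant laboratory abnormality from Day 1 into the adverse event record; 9.1.1 sets narrower conditions. An abnormality that is recorded appears by preferred term and functional severity, with no mark that it was dose-limiting or of special interest.

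6. *Listings.* Listings 14.3.2.1, 14.3.2.2, 16.2.7.1 and 16.2.7.2 have a column for serious, special-interest and dose-limiting status and another for signs of drug toxicity. The hematology, biochemistry and coagulation listings print each result with its reference range. The counts can therefore be assembled by hand. Listing 14.3.2.3 prints grade labels beside Mild and Severe but lacks the special-interest and dose-limiting column. It is inconsistent with the others and does not amount to a grading plan.

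**The case against.** The strongest reply is that the SAP does follow the protocol, on the section that governs how severity is rated. Section 9.1.6 makes the functional rating mandatory, and 10.5 also promises tabulation by severity, which the SAP delivers. This stands. The conflict starts inside the protocol, and editing the SAP alone would leave investigators rating on one scale while the report used another.

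Second, a reader might infer that the protocol promised laboratory shifts by toxicity grade. It did not. Section 10.5 and the synopsis promise shift tables without naming grades, and Low/Normal/High shifts satisfy that.

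Third, a reader might infer that serious toxicity would be invisible, with every threshold merged into one category. The documents do not support that either. The merging is confined to the laboratory shift tables. Clinical events keep three severity levels by dose, the overall summary has a row for severe events, and the listings flag what the tables omit. With 6 active subjects per dose, and a halt for related events of Grade 3 or higher, the counts will be small enough to tally by eye. This lowers the weight of the point. It does not remove it, because the primary safety tables should not depend on a hand count.

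Fourth, the FDA grading tables are not reproduced in the documents, so which laboratory parameters can be graded is not known here. The criterion of more than 5 x ULN for over 2 weeks cannot be observed on scheduled samples in Cohorts 1 to 3, which end at Day 8. Both limits stand and belong in the table footnotes.

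**Conclusion.** The point holds, within limits. One protocol element, toxicity grading of adverse events, is missing from the SAP without being declared, and the protocol itself carries two scales that have not been reconciled. As a result, no planned summary table gives, for any of the three doses or for pooled placebo, the number of subjects who met the dose-limiting, special-interest or ULN-multiple criteria.

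It would go too far to say that these events define tolerability or that escalation is compromised. The safety review committee judges tolerability from the accruing safety data, not from these tables, and a count of dose-limiting events is not among the primary endpoints. What is lost is ready reporting by dose; the data remain available.

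This rests on two assumptions: that Attachment 1 is the full set of planned tables, and that the special-interest and dose-limiting flags in the listing shells are collected as shown. It is worth correcting and does not threaten the study.

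**What to change.** - **Scale.** Reconcile Protocol 9.1.4, 9.1.6 and 10.5 with SAP 4.1.2 and 6.8.2, so that it is clear which scale is recorded, which is derived and which each table uses. Otherwise declare and justify the departure in SAP 7.1. Bring the Listing 14.3.2.3 shell into line with the others.
- **Event table (SAP 6.8.2).** Add one table, by dose and pooled placebo, of subjects with any dose-limiting event, any event of special interest and any event of Grade 3 or higher.
- **Liver table (SAP 6.8.3).** Add one table of worst post-dose ALT/AST in ULN-multiple categories, including the combined bilirubin/INR criterion of Protocol 9.1.5. A footnote should say which criteria the scheduled sampling cannot capture.
- **Supplementary.** Laboratory shifts from baseline grade to worst post-dose grade, for the parameters the scale covers. This would be an improvement and does not repair a broken commitment.

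The cost is a derived grade variable and two or three tables, built largely on flags, results and reference ranges already planned for the listings. Many cells will hold zero or one subject, so the tables should be read as counts and not as rates.

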## 10.6 PK Analysis

Descriptive statistics for PK concentrations and parameters will consist of number of subjects (n), arithmetic mean, standard deviation (SD), geometric mean, geometric coefficient of variation (%), median, minimum, and maximum. For  $T_{max}$  and  $T_{1/2}$ , only n, median, minimum, and maximum will be presented.

This study will perform PK analysis using validated software, such as Phoenix® WinNonlin® version 8.0 or higher. Pharmacokinetic parameters will be calculated through noncompartmental analysis of fenretinide and its metabolites MPR and oxo-HPR, including  $C_{max}$ ,  $AUC_{last}$ ,  $AUC_{inf}$ ,  $T_{max}$ ,  $T_{\frac{1}{2}}$ , Cl/F, and V/F on the day of dosing. Other relevant parameters will also be estimated.

Dose proportionality for fenretinide exposure parameters ( $C_{max}$ ,  $AUC_{last}$ , and  $AUC_{inf}$ ) will be assessed statistically based on the natural log (ln)-transformed PK parameters. Proportionality analysis will be done using a Power Model defined as:

$$\ln (PK \text{ parameter}) = \alpha + \beta \cdot \ln (Dose) + \varepsilon$$

where  $\alpha$  is the intercept,  $\beta$  is the slope, and  $\epsilon$  is the error term. A linear model with ln-transformed dose as a continuous effect will be fitted. A point estimate and a 90% CI will be derived for the slope ( $\beta$ ), measure of the proportionality between the dose and the PK parameter. Evidence of dose proportionality for each PK parameter evaluated will be assessed by the 90% CI of each slope.

Appropriate dose-normalized PK parameters will also be assessed graphically for dose proportionality.

An ANOVA will be conducted on ln-transformed PK parameters, including  $AUC_{last}$ ,  $AUC_{inf}$ , and  $C_{max}$  to evaluate the effect of food on fenretinide in the recalled cohort (Cohort 4 vs Cohort 3). The study will calculate the differences between adjusted means and the standard error associated with these differences. The ratio of means will be calculated using the LSM for ln-transformed  $AUC_{last}$ ,  $AUC_{inf}$ , and  $C_{max}$  values. The 90% confidence interval (CI) for the difference between the fed and fasted conditions will be calculated for  $AUC_{last}$ ,  $AUC_{inf}$ , and  $C_{max}$  using ln-transformed concentration data. The CI will be expressed as a percentage relative to the LSM.

## 11 QUALITY CONTROL AND ASSURANCE

Each clinical site will be responsible for internal quality management of study conduct, data and biological specimen collection, documentation, and completion based on their internal processes.

Quality control procedures will be implemented beginning with the data entry system and data quality control checks that will be run on the database to generate queries to the site(s) where applicable. Any missing data or data anomalies will be communicated to the site(s) for clarification/resolution.

Following written Standard Operating Procedures and the Clinical Monitoring Plan, the monitors will verify that the clinical trial is conducted, that data are generated, documented (recorded), and reported, and that biological specimens are collected in compliance with the protocol, International Council for Harmonisation (ICH) Good Clinical Practice (GCP), and applicable regulatory requirements (e.g., Good Laboratory Practices and GMP).

The investigational site will provide direct access to all study-related locations, source data/documents, and reports for the purpose of monitoring and auditing by the Sponsor and inspection by local and regulatory authorities.

#### 12 REGULATORY AND ETHICAL CONSIDERATIONS

# 12.1 Institutional Review Board or Independent Ethics Committee Approval

The protocol, ICF, Investigator's Brochure, and other relevant documents (eg, advertisements) must be submitted to an HREC by the Investigator and be reviewed and approved by the HREC before the study is initiated.

Any amendments to the protocol will require HREC approval before implementation of changes made to the study design.

The Investigator will provide written summaries of the status of the study to the HREC annually or more frequently in accordance with the requirements, policies, and procedures established by the HREC. The Investigator will also notify the HREC of SAEs or other significant safety findings as required by HREC procedures.

## 12.2 Ethical Conduct of the Study

This study will be conducted in accordance with the protocol and with the following:

- current Declaration of Helsinki (Ethical Principles for Medical Research Involving Human Subjects) National Health and Medical Research Council National Statement on Ethical Conduct in Human Research 2007 (updated 2018).
- International Council for Harmonisation (ICH) Integrated Addendum to E6(R1): Guideline for Good Clinical Practice (GCP) ICH E6(R2), annotated with comments by the Australian Therapeutic Goods Administration (2018).
- Applicable laws and regulations.

## 12.3 Subject Information and Consent

Consent forms that describe the study drug, study procedures, and risks will be given to each potential subject and the nature and purpose of the study shall be fully explained. Written documentation of informed consent must be obtained from each subject prior to any study procedures being performed.

Informed consent is a process that is initiated prior to the individual's agreeing to participate in the study and continues throughout the individual's study participation. Consent forms will be approved by the HREC, and the subject will be asked to read and review the document. Consent forms must be in a language fully comprehensible to the prospective subject. The Investigator (or designee as per local regulation) will explain the research study to the subject and answer any questions that may arise. A verbal explanation will be provided in terms suited to the subject's comprehension of the purposes, procedures, and potential risks of the study and of their rights as research subjects.

Subjects will have the opportunity to carefully review the written ICF and ask questions prior to signing. The subjects should have the opportunity to discuss the study with their family or

surrogates or think about it prior to agreeing to participate. Subjects must be informed that participation is voluntary and that they may withdraw from the study at any time, without prejudice. A copy of the informed consent document will be given to the subject for their records.

The informed consent process will be conducted and documented in the subject's medical records (including the date), as required by the ICH Integrated Addendum to ICH E6(R1): Guideline for GCP E6(R2), as adopted by the Australian Therapeutic Goods Administration (TGA), and the NHMRC National Statement on Ethical Conduct in Human Research.. Electronic media may be used to replace paper-based informed consent processes (electronic informed consent), utilizing electronic signatures. An electronic informed consent may be used to provide the same information that is contained within the written informed consent document, evaluate the subject's comprehension of the information presented, and document the consent of the subject. The rights and welfare of the subjects will be protected by emphasizing to them that the quality of their medical care will not be adversely affected if they decline to participate in this study.

The informed consent form should be updated or amended whenever new important information that may be relevant to the subject becomes available. Modifications must be approved by the Sponsor and by the HREC before being implemented.

## 12.4 Subject Confidentiality

Subject confidentiality and privacy are strictly held in trust by the participating Investigators, their staff, and the Sponsor. This confidentiality is extended to cover testing of biological samples and genetic tests in addition to the clinical information relating to subjects. Therefore, the study protocol, documentation, data, and all other information generated will be held in strict confidence. No information concerning the study, or the data will be released to any unauthorized third party without prior written approval of the Sponsor.

The study monitor, other authorized representatives of the Sponsor, representatives of the HREC, or regulatory agencies may inspect all documents and records required to be maintained by the Investigator, including but not limited to, medical records (office, clinic, or hospital) and pharmacy records for the subjects in this study. The clinical study site will permit access to such records.

The study subject's contact information will be securely stored at each clinical site for internal use during the study. At the end of the study, all records will continue to be kept in a secure location for as long a period as is dictated by the reviewing HREC, institutional policies, regulatory authorities, or Sponsor requirements.

Subject research data for purposes of statistical analysis and scientific reporting will be transmitted to and stored in the IBM Clinical Development database. A subject's contact or identifying information will not be included.

